#### **5.2.3.2 Phase II**

Following the study schema (Figure 2) patients are expected to complete 28 days of study treatment followed by surgery for the “window option”, with an off study visit after surgery, and will be monitored for adverse events up to 30 days after the last dose of study drug.

Patients whose tumors at T1 biopsy show Ki67 > 10% will be required to come off study and per standard of care would typically be recommended to proceed to definitive surgery or standard neoadjuvant chemotherapy. All other patients will continue on study therapy and at T2 (week 5, or day 29), will proceed with definitive surgery or undergo a research biopsy and continue with standard of care neoadjuvant endocrine therapy or chemotherapy as clinically indicated.

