### **3.6 Phase II Patient Evaluability**

Patients who meet the eligibility criteria and complete a full 4 weeks of therapy (14 days of low-dose palbociclib plus letrozole and 14 days of dose palbociclib plus letrozole with HCQ) will be considered evaluable for Phase II. In addition, the completion of biopsies at T0, T1 and T2 with interpretability of Ki67 are required for evalutability. Baseline Ki67 >5% is required to enhance the interpretability of CCCA fraction change from T1 to T2.

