### **3.7 Replacement of Patients**

Patients who are not evaluable for dose-limiting toxicity in the Phase I portion and those not evaluable for Ki67 at T0, T1 and T2 in the Phase II portion will be replaced.

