### **3.8 Target Accrual**

A total of 54 patients will be enrolled to the study. This includes 2 to 18 patients (up to 6 per dose cohort at 400, 600 and 800 mg of HCQ daily and 6 at the RP2D, but as few as 2 patients in the unlikely event that the first 2 patients experience DLT at the lowest dose of HCQ (400 mg daily) and the study is halted.) in the Phase I metastatic portion, 6 patients for neo-adjuvant Phase II Part 1 and 30 patients for the Phase II Part 2 portion (25 needed for statistical plan and 5 expected to drop out). This does not account for replaced patients (as stated in Sections 3.6 and 3.7).

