C= Phase I – baseline biopsy can of metastatic tumor pre-treatment or primary lesion (optional) or can be from archival tissue if available (either primary or metastasis). Week 5 biopsy (optional) can be +/- 1 week. Phase II – biopsies are mandatory- third biopsy done either at W5 for patients going on to surgery at that time, for those waiting until between weeks 20-24, biopsy done pre-operatively. Patients who know in advance that they will proceed with surgery at T2 will not need a biopsy and biomarkers will be measured on the surgical specimen. Imaging will be done at end of Cycle 2 (Week 8) +/- 1 week (prior to cycle 3 drug), and every 8-12 weeks (+/- 2 weeks) thereafter

D= Phase II – Sample of surgical specimen (or core needle biopsy if patients is going on to standard of care neoadjuvant endocrine or chemotherapy) will be taken for analysis as outlined in Section 5.3.

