### **Phase II:**

The Phase II portion will be performed in a different population of patients (early stage) in the pre-operative setting. In order to obtain qualitative information about the dose responsiveness of HCQ when added to letrozole and palbociclib, Part 1 of the Phase II portion will enroll 6 patients at an HCQ dose of 400 mg (if in fact, the RP2D is 600 or 800 mg). Following this, Part 2 will be conducted at the RP2D for HCQ based on the primary endpoint of proportion of patients achieving tumoral CCCA, with the formal statistical plan using a 2-stage Simon optimal design and looking to increase the CCCA rate from 50% with low dose palbociclib + letrozole to 75% after the addition of HCQ. This design requires 11 patients in the first stage and 14 patients in the 2nd stage. It would stop after the 1st stage if no more than 6 patients show CCCA by tumor biopsy after HCQ treatment and declared the treatment as promising if at least 17 out of 25 total evaluable patients exhibit CCCA.

This design has alpha = 4%, 81% power, and a probability of 0.73 of terminating after the 1st stage if the true CCCA rate=50%. For the group of patients at the RP2D, we therefore plan a sample size of 30 patients over 12-15 months, accounting for patient dropout (including those with Ki67 >10% at T1). We have a large eligible patient population and have led national accruals in other multi-center neoadjuvant endocrine trials in post-menopausal women (e.g. ALTERNATE Trial). In addition, recent local experience of conducting window of opportunity trials in this setting have demonstrated the feasibility of accrual at a rate of ~2 patients per month. Thus, we expect to achieve accrual goals.

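### Footnote C, read literally, moves deferring patients' third Phase II biopsy from day 29 to weeks 20-24, and the protocol contradicts itself on treatment after day 29

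*Combined protocol and SAP*

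**What the plan says.** **T2 biopsy.** Section 2.2.3 compares complete cell cycle arrest at T1 (week 2) with T2 (day 29). Section 3.5 takes T2 after four weeks, from the surgical specimen or from a research biopsy at the same point if more neoadjuvant therapy is indicated. Section 5.2.3.2 says that at day 29 every patient still on study "will proceed with definitive surgery or undergo a research biopsy and continue with standard of care neoadjuvant endocrine therapy or chemotherapy as clinically indicated". The W5 biopsy cell of Table 2 carries footnote D, which asks for a surgical sample or a "core needle biopsy if patients is going on to standard of care neoadjuvant endocrine or chemotherapy".

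**Footnote C.** In its Phase II part, the note places the "third biopsy done either at W5 for patients going on to surgery at that time" and adds: "for those waiting until between weeks 20-24, biopsy done pre-operatively".

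**Evaluability.** Under 3.6, "the completion of biopsies at T0, T1 and T2 with interpretability of Ki67 are required for evalutability". Under 3.7, "those not evaluable for Ki67 at T0, T1 and T2 in the Phase II portion will be replaced". Section 3.8 describes the 30 Part 2 patients as "25 needed for statistical plan and 5 expected to drop out", and Section 8.0 describes the same margin as "accounting for patient dropout (including those with Ki67 >10% at T1").

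**After day 29.** One paragraph of 1.3 lets patients whose proliferation is suppressed at both the 2- and 4-week biopsies remain on treatment for a course of 16-24 weeks. Sections 1.4, 5.2.2 and 5.3.2 speak of remaining on study until surgery, and 2.2.2 and 2.2.4 set objectives for extended pre-operative therapy of up to 24 weeks. Against this, a bullet in 1.3 describes four weeks of study drug followed by standard of care, 5.2.3.2 sends patients not operated on at T2 to standard of care, and the drug rows of Table 2 stop at W4.

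**The concern.** T2 carries both the primary endpoint and evaluability, so an instruction that moves it for some patients matters even when it sits in a footnote. A site following footnote C would take no day-29 tissue from a patient who defers surgery. That patient would be lost to the primary analysis and replaced, so the evaluable set would lean towards patients operated on at week 5. The site would also lack the 4-week result that 1.3 uses to decide who may stay on treatment. If the pre-operative sample were used as T2 instead, Ki67 would be read after months of therapy that the text does not name.

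The drug question affects safety and the long-term objectives. Section 5.2.3.1 caps Phase I treatment at one year because HCQ toxicity may depend on duration. Adverse-event follow-up runs to 30 days after the last dose of study drug, so investigators need to know when that dose is. If some patients continue the triplet while others move to standard therapy, long-term response under 2.2.2 and 2.2.4 would mix two treatments.

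**Working it through.** **The plan's own figures.** Part 2 needs 11 + 14 = 25 evaluable patients, and 25 + 5 = 30, as stated. The rule is to stop at 6 or fewer of 11 and to succeed at 17 or more of 25.

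- Early termination at 50%: P(Bin(11, 0.5) ≤ 6) = 0.7256 (plan: 0.73).
- Power at 75%: the sum over x = 7 to 11 of P(Bin(11, 0.75) = x) × P(Bin(14, 0.75) ≥ 17 − x) = 0.8005 (plan: 81%).
- The same sum at 50% gives alpha = 0.0458 (plan: 4%), a separate matter.

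Because 3.7 replaces non-evaluable patients, the analysed number stays at 25 and footnote C does not lower nominal power. The cost is accrual and selection. The margin of 5 of 30 (16.7%) is already allotted to dropout, including T1 Ki67 above 10%.

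**When does a deferring patient have the third biopsy?**

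| Source | Timing |
|---|---|
| 2.2.3 | T2 at day 29 |
| 3.2.2, Figure 2 legend | surgery right after T2 or up to 24 weeks, so T2 comes before deferral |
| 3.5 | research biopsy at the four-week point |
| 5.2.3.2; Table 2 W5 cell with footnote D | day 29 |
| 1.3 | 4-week biopsy decides who may stay on |
| Footnote C | pre-operatively, for those waiting until weeks 20-24 |

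**Size of the shift.** In Table 2, W5 is day 29, so week k starts on day 7(k − 1) + 1.

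- Earliest: week 20 starts on day 7 × 19 + 1 = 134, and 134 − 29 = 105 days (15.0 weeks).
- Latest: 24 completed weeks is day 168, and 168 − 29 = 139 days (19.9 weeks).
- Allowed window in Table 2: ±2 days.

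Sections 1.3, 1.4 and 5.2.2 give the deferral period as weeks 16-24, so footnote C also leaves surgery in weeks 16-19 without an instruction.

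**Schedule after day 29.** Section 5.2.2 sets visits at weeks 6, 8 and every 4 weeks to surgery and refers to Table 2. That table has no column between W5 and Off Study, and laboratory tests in that interval are only as indicated.

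**Only if the triplet continues to surgery** (not stated anywhere):

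- HCQ starts on day 15, so the window gives 28 − 14 = 14 days. Continuing to week 16 gives 112 − 14 = 98 days; to week 24, 168 − 14 = 154 days.
- The palbociclib label in Appendix A asks for blood counts at each cycle start and on Day 15 of the first two cycles. After day 29 these fall on days 43, 57 and 85 (3 by day 112), plus 113 and 141 (5 by day 168). Table 2 schedules none. The weekly counts in 6.1.4 apply once grade 3 or 4 neutropenia has been found.

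**The case against.** The strongest reply is that the protocol's intent is clear. Day 29 is fixed in the endpoint definition, in 3.5, in 5.2.3.2 and in the Table 2 cell. Superscript C marks only Table 1 cells, so the Phase II sentence in that note is attached to no Phase II cell, and its grammar is broken. On treatment, 5.2.3.2 is the governing section and leads to standard of care. Remaining on study need not mean remaining on study drug, and the duration in 1.3 is that of an ordinary neoadjuvant endocrine course.

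Much of this stands. The sponsor very probably intends day 29 for everyone, and stopping study drug at T2 is the better-supported reading. But footnote C is expressly a Phase II instruction and sits beside footnote D, which tells the site the opposite. Section 1.3 offers remaining on treatment as an alternative to coming off study at four weeks, and 1.4 contrasts it with short exposure; neither fits 5.2.3.2.

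A reader might infer that the protocol says nothing about continuing palbociclib and HCQ. It does address continuation, but implicitly and in conflicting terms. A reader might also infer that no ultrasound is planned after W5, because Table 2 shows none. The Figure 2 graphic is not available here and may show ultrasound timing or drugs by period, so that absence cannot be established.

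**Conclusion.** The conflict is real and should be corrected, but it is narrow. One footnote disagrees with several passages that fix T2 at day 29. A site following it would take the third biopsy 105 to 139 days after day 29 and lose that patient from the evaluable set. It is tempting to conclude that the primary endpoint is compromised. The documents do not support that: if T2 is taken at day 29 in every patient remaining on study, the primary comparison is unaffected, and replacement preserves nominal power. Nor can the number of lost patients be estimated, because no deferral rate is given.

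On treatment after day 29 the passages disagree and no available text names the drugs. The figures of 98-154 days of HCQ and 3-5 unscheduled blood counts hold only if the triplet continues, which 5.2.3.2 does not provide for; if drug stops at T2, both fall away. The missing extension columns in Table 2 are a gap on either reading, since 5.2.2 cites them.

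**What to change.** 1. Amend footnote C so that a day-29 T2 core biopsy or surgical specimen is required for every patient remaining on study. Any later pre-operative sample is additional to T2 and never a substitute. Use one deferral window, weeks 16-24, throughout.
2. State in 5.2.3.2 that palbociclib and HCQ stop at T2, consistent with that section and Table 2, and align 1.3, 1.4, 5.2.2 and 5.3.2. If continuation is intended, say so and add scheduled blood counts and chemistry at the 5.2.2 visits to Table 2.
3. Report long-term response by the therapy actually received after day 29.

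The cost is wording and table edits, with no extra patients. The day-29 core for deferring patients is already required by 3.6 and footnote D. If the triplet is continued, the label blood-count days (43, 57, 85, 113, 141) coincide with the research draws in 5.3.2, so no draw days are added.

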#### **5.2.4 End of treatment visit and Follow up assessments**

Patients who discontinue study treatment, will be followed for 30 days after stopping the study drugs for assessment of safety (i.e., assessment of AEs and/or serious AEs [SAEs] and concomitant medications) and resolution of any treatment related toxicity. Patients continuing to experience toxicity at this point following discontinuation of treatment will continue to be followed at least every 4 weeks until resolution or determination, in the clinical judgment of the investigator, that no further improvement is expected.

#### **5.2.5 Early discontinuation**

Patients who come off trial early will be asked to return for the off-study assessments as detailed in Tables 1 and 2. In the event of a continuing AE, the patient will be asked to return for follow-up until resolution or stabilization of the AE.

#### **5.2.6 Review of Systems and Physical Exam**

A full review of systems that covers all of the domains and systems represented in CTCAE V 4.03 toxicity criteria will be performed at screening/baseline. Subsequent physical exams may be limited and should be focused on sites of disease to explore clinical signs and symptoms.

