### 5.2.3 Treatment Duration

#### 5.2.3.1 Phase I

Patients will receive treatment for at least until week 8 as long as there are no DLTs in the first 4 weeks, or significant toxicities requiring treatment discontinuation in the judgment of the treating investigator, and no evidence of clinical progression. At week 8, if tumor assessment by scans show evidence or response by RECIST 1.1 criteria (applies only to patients with

measurable disease), they will be allowed to stay on treatment as long as there is no evidence of progression or significant toxicities up to a maximum of 1 year. This maximum timeframe is due to concerns about HCQ toxicity, which could be duration-dependent. Patients who show progression or stability of disease at week 8 will come off study and can continue standard treatment (standard dose palbociclib and letrozole) or alternate therapy at the discretion of the treating physician.

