#### **6.2.3 Dosing of hydroxychloroquine and dose adjustments for hydroxychloroquine**

HCQ will be given by mouth at the assigned dose for the Phase I dose escalation and Phase II fixed dose parts of the trial. The dose of 400 mg daily was chosen as the starting dose for the Phase I portion as this is the usual dose used clinically and has been combined with endocrine and other and cancer therapies at this dose in prior studies.P34-37P There will be no dose adjustments for HCQ, and any grade 3 toxicity that is attributed to HCQ will require discontinuation of drug and for the patient to come off study. Subsequent treatment will be as per standard of care. For patients on the Phase I portion, any Grade III toxicity attributed to HCQ will also be counted as a dose-limiting toxicity if occurring in the first 28 days.

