### **39. Warnings**

**PHYSICIANS SHOULD COMPLETELY FAMILIARIZE THEMSELVES WITH THE COMPLETE CONTENTS OF THIS LEAFLET BEFORE PRESCRIBING PLAQUENIL.**

Irreversible retinal damage has been observed in some patients who had received long- term or high-dosage 4-aminoquinoline therapy for discoid and systemic lupus erythematosus, or rheumatoid arthritis. Retinopathy has been reported to be dose-related.

When prolonged therapy with any Antimalarial compound is contemplated, initial (base line) and periodic (every three months) ophthalmologic examinations (including visual acuity, expert slit-lamp, funduscopic, and visual field tests) should be performed.

If there is any indication of abnormality in the visual acuity, visual field, or retinal macular areas (such as pigmentary changes, loss of foveal reflex), or any visual symptoms (such as light flashes and streaks) which are not fully explainable by difficulties of accommodation or corneal opacities, the drug should be discontinued immediately and the patient closely observed.

for possible progression. Retinal changes (and visual disturbances) may progress even after cessation of therapy.

All patients on long-term therapy with this preparation should be questioned and examined periodically, including the testing of knee and ankle reflexes, to detect any evidence of muscular weakness. If weakness occurs, discontinue the drug.

In the treatment of rheumatoid arthritis, if objective improvement (such as reduced joint swelling, increased mobility) does not occur within six months, the drug should be discontinued. Safe use of the drug in the treatment of juvenile arthritis has not been established.

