## 41. Adverse Reactions

Not all of the following reactions have been observed with every 4-aminoquinoline compound during long-term therapy, but they have been reported with one or more and should be borne in mind when drugs of this class are administered. Adverse effects with different compounds vary in type and frequency.

**CNS Reactions:** Irritability, nervousness, emotional changes, nightmares, psychosis, headache, dizziness, vertigo, tinnitus, nystagmus, nerve deafness, convulsions, ataxia.

**Neuromuscular Reactions:** Skeletal muscle palsies or skeletal muscle myopathy or neuromyopathy leading to progressive weakness and atrophy of proximal muscle groups which may be associated with mild sensory changes, depression of tendon reflexes and abnormal nerve conduction.

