## 42. Dosage and Administration

One tablet of hydroxychloroquine sulfate, 200 mg, is equivalent to 155 mg base.

**Lupus erythematosus**—Initially, the average **adult** dose is 400 mg (=310 mg base) once or twice daily. This may be continued for several weeks or months, depending on the response of the patient. For prolonged maintenance therapy, a smaller dose, from 200 mg to 400 mg (=155 mg to 310 mg base) daily will frequently suffice.

The incidence of retinopathy has been reported to be higher when this maintenance dose is exceeded.

**Rheumatoid arthritis**—The compound is cumulative in action and will require several weeks to exert its beneficial therapeutic effects, whereas minor side effects may occur relatively early. Several months of therapy may be required before maximum effects can be obtained. If objective improvement (such as reduced joint swelling, increased mobility) does not occur within six months, the drug should be discontinued. Safe use of the drug in the treatment of juvenile rheumatoid arthritis has not been established.

**Initial dosage**—In **adults**, from 400 mg to 600 mg (=310 mg to 465 mg base) daily, each dose to be taken with a meal or a glass of milk. In a small percentage of patients, troublesome side effects may require temporary reduction of the initial dosage. Later (usually from five to ten days), the dose may gradually be increased to the optimum response level, often without return of side effects.

**Maintenance dosage**—When a good response is obtained (usually in four to twelve weeks), the dosage is reduced by 50 percent and continued at a usual maintenance level of 200 mg to 400 mg (=155 mg to 310 mg base) daily, each dose to be taken with a meal or a glass of milk. The incidence of retinopathy has been reported to be higher when this maintenance dose is exceeded.

Should a relapse occur after medication is withdrawn, therapy may be resumed or continued on an intermittent schedule if there are no ocular contraindications.

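### Phase I responders may take HCQ for up to 1 year, but no text requires the check for muscular weakness that the appended label asks for on long-term therapy, and 5.2.6 points on-treatment exams at sites of disease

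*Combined protocol and SAP*

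**What the plan says.** - **Duration.** Under 5.2.3.1, responders at week 8 with measurable disease are "allowed to stay on treatment as long as there is no evidence of progression or significant toxicities up to a maximum of 1 year". The section gives its reason for the cap: "This maximum timeframe is due to concerns about HCQ toxicity, which could be duration-dependent". Patients with stable or progressive disease at week 8 come off study.
- **Exam content.** Section 5.2.6 requires a full review of systems across the CTCAE domains at screening/baseline. It then says: "Subsequent physical exams may be limited and should be focused on sites of disease to explore clinical signs and symptoms".
- **Schedule.** Table 1 places a physical exam and an adverse event assessment at every Phase I visit, including C3, C4+ and off study. It has no row or footnote for muscle strength or reflexes.
- **Stopping.** Section 6.2.3 says: "There will be no dose adjustments for HCQ, and any grade 3 toxicity that is attributed to HCQ will require discontinuation of drug". Below grade 3, 5.2.3.1 relies on a judgment that toxicity is significant. Neither section names weakness.
- **Label.** Appendix B, Warnings (lupus and rheumatoid arthritis section), says: "All patients on long-term therapy with this preparation should be questioned and examined periodically, including the testing of knee and ankle reflexes", and gives the purpose and action: "to detect any evidence of muscular weakness. If weakness occurs, discontinue the drug". Its Adverse Reactions section lists myopathy and neuromyopathy with progressive proximal weakness, which may come with "depression of tendon reflexes and abnormal nerve conduction".

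**The concern.** The protocol caps treatment at 1 year because it suspects that HCQ toxicity may grow with exposure. For the patients who approach that cap, however, its only rule on exam content directs the examiner to the tumor. The appended label describes a specific bedside check for a specific toxicity and attaches a stop instruction to it. The body of the protocol cites Appendix B only for further detail (6.2.1) and does not tell sites to follow its monitoring.

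At stake is the safety of a few patients on prolonged HCQ. A responder could develop early proximal weakness, not mention it or put it down to tiredness, and stay on the drug because no scheduled exam had to look for it. Symptoms alone are hard to attribute on this regimen: Appendix A, Table 4, reports fatigue in 37% and asthenia in 17% of patients on palbociclib plus letrozole, at the higher 125 mg/d palbociclib dose.

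**Working it through.** The plan gives no figure to reproduce. The check sets texts side by side, followed by simple counts for scale.

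**1. Is the check required anywhere in Phase I?**

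| Place | What it provides | Requires strength or reflex testing? |
|---|---|---|
| 2.1.1 | Continuous CTCAE V4.03 safety assessment with physical examination and laboratory tests | No |
| Table 1 | Exam and adverse event assessment at every visit | No |
| 5.2.2 | Organ-specific review of systems on treatment | No; Phase II only |
| 5.2.6 | Full review at baseline, then a limited exam focused on disease sites | No |
| 5.2.7 | Laboratory panel; AST is included but is not specific to muscle | No |
| 6.2.3 | Stop HCQ at attributed grade 3 toxicity | No |
| 7.4 | Adverse events found by questioning, examination or other means are reported | No |

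HCQ eye toxicity, by contrast, has scheduled exams in Table 1 at baseline and off study.

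**2. How do the stopping texts compare?** The label says to stop if weakness occurs, with no grade threshold. The protocol mandates stopping at attributed grade 3 and leaves lower grades to judgment.

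**3. What does existing monitoring leave uncovered?** Reported weakness should surface through 2.1.1, Table 1 and 7.4. A depressed tendon reflex, or mild weakness the patient has not noticed, needs an examination to find it.

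**4. Exposure and exams after week 8.** Cycles are 28 days (Design for the Safety Component/Phase I).
- HCQ days after week 8 for a patient completing 1 year: 365 − 56 = 309.
- C3 D1 is day 2 × 28 + 1 = 57. C13 D1 is day 12 × 28 + 1 = 337. C14 D1 is day 13 × 28 + 1 = 365, the last day, and is not counted.
- Exams from C3 to C13: 13 − 3 + 1 = 11. This assumes that the C4+ column in Table 1 means day 1 of each later cycle, which the table does not spell out.

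**5. Number of patients.** Section 3.8 allows up to 6 at each of three HCQ doses: 3 × 6 = 18, before replacements. Only responders with measurable disease continue, and 5.2.8 also admits patients with bone lesions alone. The documents do not say how many will continue. As an illustration only:
- Assumed measurable share, from label Study 1 (Appendix A, Table 8): 338/444 = 76.1%.
- Assumed response by week 8: 10% (a chosen floor) to 55.3% (the Study 1 rate, a ceiling because it was seen at 125 mg/d palbociclib and at any time).
- Continuing patients, if all 18 enroll: 18 × 0.761 × 0.10 = 1.4, to 18 × 0.761 × 0.553 = 7.6.

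The documents give no frequency for neuromyopathy, so the number of cases the check would find cannot be estimated.

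**The case against.** The strongest reply is that Phase I already monitors safety closely. Safety is its primary endpoint, assessed continuously with physical examination, and every visit includes adverse event assessment. Section 5.2.6 sets a minimum and does not bar a wider exam. The full label is appended, and it warns physicians to know its contents. Most of this stands. A reader might infer that Phase I lacks neuromuscular safety monitoring, or that 5.2.6 forbids the check; the documents support neither. What remains is that 5.2.6 gives an explicit direction, and it leads away from the label's check.

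Second, the label's stop instruction depends on weakness, not on reflex loss. That is right: an isolated reflex change would not by itself stop HCQ under the label. Reflex testing is nonetheless the means of detection that the label names.

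Third, the label text sits in the lupus and rheumatoid arthritis section and leaves long-term undefined. A reader might infer that the protocol breaches the label. That goes too far. Treating up to 1 year as long-term is a judgment, supported by the protocol's own worry about duration but not settled by it.

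A reader might also infer a neuromuscular dose problem, since the label recommends 200 to 400 mg daily for prolonged maintenance and the protocol allows no HCQ dose adjustment. The label ties exceeding that maintenance dose to retinopathy, so it does not bear on this point. The top dose of 800 mg/d also lies within the initial lupus range of 400 mg once or twice daily, of which the label says: "This may be continued for several weeks or months, depending on the response of the patient".

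**Conclusion.** The point holds as a minor patient-safety gap. For Phase I responders who continue HCQ beyond week 8, no text requires an examination for muscular weakness, and 5.2.6 points the exam elsewhere. The gap is mainly weakness that the patient does not report and only examination would show.

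The affected group is an unknown subset of at most 18 planned patients, each with up to 309 further days on HCQ. The conclusion rests on one judgment, that up to 1 year counts as long-term. The exam count also depends on how the C4+ column is read.

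A reader might infer that missed events could bias the dose decision. The documents do not support that: dose-limiting toxicity is assessed in the first 28-day cycle, before the period at issue. The recommended Phase II dose, the Simon design and the Phase II endpoint are unaffected.

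**What to change.** 1. In 5.2.6, have later exams *focused on sites of disease and on systems affected by reported symptoms or expected study-drug toxicities*.
2. Add a Table 1 footnote: for Phase I patients who continue HCQ beyond week 8, test proximal muscle strength and knee and ankle reflexes at the scheduled physical exams from C3 D1, and discontinue HCQ if muscular weakness occurs. Keep the stop rule as unqualified as the label's. State in the same footnote that C4+ means day 1 of each later cycle, if that is the intent.

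The cost is one sentence and one footnote, with no new visits. Expect a few minutes per exam (an estimate; the documents give no timing) at about 11 exams for a patient who completes the year. Some extra low-grade events will be recorded, and an occasional responder may stop HCQ earlier than otherwise.
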